1.1 Scope of Document

The Statistical Analysis Plan (SAP) describes the implementation of the planned statistical analysis that will be included in the Clinical Study Report (CSR) for protocol No. AV002: A phase 2b randomized, double-blind, placebo controlled, multicenter 12-week study with an additional 40-week follow-up assessment of efficacy, safety and tolerability of M1095 in subjects with moderate to severe chronic plaque-type psoriasis.

1.2 Study Reference Documentation

Final study protocol (Version 3.0, incorporating CZE-1, dated 16th October 2018) is available at the time of finalization of the SAP.

1.3 Study Objectives

1.3.1 Primary Objective

Type of Objective	Study Objective
Primary Objective	
 To evaluate the efficacy of four dose regimens of M1095 compared to placebo on achievement of an Investigator's Global Assessment (IGA) score of 0 or 1 after 12 weeks of treatment in subjects with moderate to severe chronic plaque-type psoriasis.

1.3.2 Secondary Objectives

Type of Objective	Study Objective
Key Secondary Objectives	
 To evaluate the efficacy of four dose regimens of M1095 compared to placebo during a 12-week treatment period on secondary endpoints: Psoriasis Area and Severity Index (PASI) 75, PASI 90, PASI 100, change in PASI and shift in IGA.
Secondary Objectives	
 To assess the dose-regimen efficacy relationship for M1095 after 12, 24, 36 and 48 weeks of treatment. To evaluate the longer-term efficacy of M1095 at Week 24 and at Weeks 36 and 48. To assess the safety and tolerability of M1095.

1.3.3 Exploratory Objectives

Type of Objective	Study Objective
Exploratory Objectives	
 Assessment of the quality of life and health outcomes of subjects treated with M1095 over 48 weeks via quality of life instruments evaluated every 12 weeks. Assessment of the population pharmacokinetics (PK) of various doses and dose regimens of M1095. Assessment of the development of antidrug antibodies for various doses and dose regimens of M1095. Assessment of change in efficacy from Week 12 to Week 24 in subjects who undergo dose escalation. Assessment of M1095 being withheld in subjects with an IGA score of 0 at Week 24.

1.4 Study Design

This is a multi-center, randomized phase 2b study in subjects with moderate to severe chronic plaque-type psoriasis. Approximately 300 subjects will be enrolled at approximately 60 investigator sites in North America and Europe.

At the end of the initial 4-week screening period (Week -4 to Week 0), all eligible subjects will be randomized within strata of prior biologic use (yes/no) and weight (≤ 90 kg/ > 90 kg) in a 1:1:1:1:1:1 ratio with approximately 50 subjects randomized into each of six treatment groups as shown below and in Figure 1.1:

1. Placebo at weeks 0, 1, 2, 3, 4, 6, 8, 10 / M1095 120mg at weeks 12, 14, 16 and Q4W.
2. M1095 (30 mg) at weeks 0, 2, 4, 8, 12 and Q4W.
3. M1095 (60 mg) at weeks 0, 2, 4, 8, 12 and Q4W.
4. M1095 (120 mg) at weeks 0, 2, 4, 8, 12 and Q8W.
5. M1095 (120 mg) at weeks 0, 2, 4, 6, 8, 10, 12 and Q4W.
6. Secukinumab (300 mg) at weeks 0, 1, 2, 3, 4, 8, 12 and Q4W.

After randomization at Week 0, the study will consist of:

- 3 consecutive treatment periods:
 - A: Induction: a 12-week treatment period (Week 0 to Week 12), which is placebo-controlled,
 - B: Maintenance/escalation: a 12-week maintenance/escalation period (Week 12 to Week 24) where all subjects are on active treatment,

C: Response assessment/dose hold: a 24 week response assessment/dose hold period (Week 24 to Week 48) where active treatment is withheld in subjects who have been administered M1095 during the maintenance period and have an IGA score of 0 at the start of this period i.e. at Week 24,

- followed by a final assessment period (Week 48 to Week 52) for safety/efficacy follow-up.

The study will be double-blinded, subject- and investigator- blinded, during all treatment periods up to Week 52 (refer to the unblinding plan for further information about the timepoints when specific teams will be unblinded during the study). Blinding will be maintained prior to Week 52 using masking techniques. Therefore, up to Week 24, subjects randomized to 30 and 60 mg M1095 (Arms 2 and 3) will be administered placebo at Weeks 1, 3, 6, 10 and 14 in order to preserve the blinding. Similarly, subjects randomized to 120 mg M1095 (Arm 4) will receive placebo at Weeks 1, 3, 6, 10, 14 and 16 and subjects randomized to 120 mg M1095 (Arm 5) will receive placebo at Weeks 1, 3 and 14. Subjects randomised to Secukinumab (Arm 6) will receive placebo at Weeks 6, 10 and 14.

At the end of the treatment induction period (Week 12), the subjects randomized to 30 mg or 60 mg M1095 who do not achieve an IGA score of 0 or 1 will be dose-escalated to 120 mg Q4W at Week 12.

Subjects who enter the maintenance/escalation period will receive one of the following treatments until Week 24 and before the dose injection at Week 24:

- **Placebo at weeks 0, 1, 2, 3, 4, 6, 8, 10** and M1095 120 mg at weeks 12, 14, 16 and Q4W.
 - **M1095 30 mg at weeks 0, 2, 4, 8, 12** and Q4W
 - **M1095 60 mg at weeks 0, 2, 4, 8, 12** and Q4W
 - **M1095 30 mg at weeks 0, 2, 4, 8** and M1095 120 mg at week 12 and Q4W
 - **M1095 60 mg at weeks 0, 2, 4, 8** and M1095 120 mg at week 12 and Q4W
 - **M1095 120 mg at weeks 0, 2, 4, 8, 12** and Q8W
 - **M1095 120 mg at weeks 0, 2, 4, 6, 8, 10, 12** and Q4W
 - **Secukinumab 300 mg at weeks 0, 1, 2, 3, 4, 8, 12** and Q4W.
- } if IGA_{Week12} ≤ 1
- } if IGA_{Week12} > 1

At the end of the maintenance/escalation period (Week 24), any subjects on M1095 treatment groups who did not undergo dose escalation at Week 12 and achieve an IGA score of 0 at Week 24 will have the study treatment withheld. To maintain the blinding after Week 24, these subjects will receive placebo Q4W. Subjects receiving secukinumab in the first treatment period will continue to receive it at the same dose 300 mg Q4W throughout the study.

[figure not shown]
Subjects who enter the response assessment/dose hold period will receive one of the following treatments until Week 44 (or until when the IGA score of subjects with M1095

treatment held at Week 24 subsequently increases to 1 or more* at which time these subjects will be re-administered the study treatment M1095 at the dose they received prior to Week 24):

- | | | |
|--|---|------------------------------|
| 
 • Placebo at weeks 0, 1, 2, 3, 4, 6, 8, 10 and M1095 120 mg at weeks 12, 14, 16 and Q4W | } | if IGA _{Week24} > 0 |
|--|---|------------------------------|
- | | | |
|---|---|------------------------------|
| 
 • Placebo at weeks 0, 1, 2, 3, 4, 6, 8, 10 and M1095 120 mg at weeks 12, 14, 16 and Q4W until Week 20 and Placebo Q4W* | } | if IGA _{Week24} = 0 |
|---|---|------------------------------|
- | | | |
|--|---|--|
| 
 • M1095 30 mg at weeks 0, 2, 4, 8, 12, and Q4W until Week 20 and Placebo Q4W* | } | if IGA _{Week12} ≤ 1 and IGA _{Week24} = 0 |
|--|---|--|
- | | | |
|--|---|--|
| 
 • M1095 60 mg at weeks 0, 2, 4, 8, 12, and Q4W until Week 20 and Placebo Q4W* | } | if IGA _{Week12} ≤ 1 and IGA _{Week24} = 0 |
|--|---|--|
- | | | |
|--|---|--|
| 
 • M1095 30 mg at weeks 0, 2, 4, 8, 12 and Q4W | } | if IGA _{Week12} ≤ 1 and IGA _{Week24} > 0 |
|--|---|--|
- | | | |
|--|---|--|
| 
 • M1095 60 mg at weeks 0, 2, 4, 8, 12 and Q4W | } | if IGA _{Week12} ≤ 1 and IGA _{Week24} > 0 |
|--|---|--|
- | | | |
|---|---|------------------------------|
| 
 • M1095 30 mg at weeks 0, 2, 4, 8 and M1095 120 mg at week 12, and Q4W | } | if IGA _{Week12} > 1 |
|---|---|------------------------------|
- | | | |
|---|---|------------------------------|
| 
 • M1095 60 mg at weeks 0, 2, 4, 8 and M1095 120 mg at week 12, and Q4W | } | if IGA _{Week12} > 1 |
|---|---|------------------------------|
- | | | |
|---|---|------------------------------|
| 
 • M1095 120 mg at weeks 0, 2, 4, 8, 12 and Q8W until Week 20, and Placebo Q4W* | } | if IGA _{Week24} = 0 |
|---|---|------------------------------|
- | | | |
|--|---|------------------------------|
| 
 • M1095 120 mg at weeks 0, 2, 4, 6, 8, 10, 12 and Q4W until week 20, and Placebo Q4W* | } | if IGA _{Week24} = 0 |
|--|---|------------------------------|
- | | | |
|---|---|------------------------------|
| 
 • M1095 120 mg at weeks 0, 2, 4, 8, 12 and Q8W | } | if IGA _{Week24} > 0 |
|---|---|------------------------------|
- | | | |
|--|---|------------------------------|
| 
 • M1095 120 mg at weeks 0, 2, 4, 6, 8, 10, 12 and Q4W | } | if IGA _{Week24} > 0 |
|--|---|------------------------------|
- **Secukinumab 300 mg at weeks 0, 1, 2, 3, 4, 8, 12** and Q4W

*If the IGA score of these subjects subsequently increases to 1 or more at any time after Week 24, these subjects will be re-administered the study treatment M1095 at the dose they received prior to Week 24 on a Q4W regimen at the scheduled visits as per protocol until the end of the treatment period. Dose will not be withheld for a second time, irrespective of subsequent IGA scores.

Figure 1.1: Flow chart / Study Design Diagram

*** Prior to Week 24**

M1095 subjects in Arms 2 and 3 will receive placebo at Week 1, 3, 6, 10 and 14.
 M1095 subjects in Arm 4 will receive placebo at Week 1, 3, 6, 10, 14 and 16.
 M1095 subjects in Arm 5 will receive placebo at Week 1, 3 and 14.
 Secukinumab subjects in Arm 6 will receive placebo at Week 6, 10 and 14.

Exposure to Placebo will be limited to a maximum of 12 weeks during the induction period and a maximum of 20 weeks after Week 24 (i.e. during the response assessment/dose hold period) provided that the subjects maintain a complete remission (i.e. achieving an IGA = 0).

All subjects, irrespective of whether they completed or discontinued the study, will be followed up for safety and potential sustainability of efficacy, for an additional 8 weeks (56 days) after receiving the last dose of study treatment. In addition, subjects who discontinued prior to Week 52 will be contacted monthly as per the study schedule (up to Week 52) to report any AEs, concomitant medications and any new psoriasis treatments.

2 Interim Analyses

Two Interim Analyses (IAs) are planned during this trial:

1. IA1: the first unblinded IA of complete 12-week data for all randomized subjects will occur at the end of the induction period, while the study is still ongoing,
2. IA2: the second IA will occur at the completion of the maintenance/escalation period at Week 24, while the study is still ongoing.

The purpose of both interim analyses is to closely monitor the safety and tolerability data throughout the study. The study will not be terminated early on the basis of either positive efficacy or futility after the review of the first or the second interim analyses. The two interim analyses are also conducted to gather preliminary efficacy information to make possible executive decisions concerning the clinical project.

The first unblinded IA will be managed by an independent Data Monitoring Committee (DMC) and an independent Data Analysis Group (DAG) to preserve the blinding. This data will be shared with firewalled individuals who are not directly involved in the conduct of the study. The DMC will be operational prior to enrolment of the first subject into the study. The composition and operation of the DMC will be described in a DMC charter. The charter will also detail how the communication between the DMC and the sponsor will be firewalled to preserve the blinding and integrity of the study. The analyses that will be included in the first interim analysis are described in Table 2.1 (refer to the corresponding sections of this SAP for further information about the analyses and to Table 4.4 for the imputation methods to be used for each assessment of this planned interim analysis). Unblinded results of IA1 will be reviewed by the DMC members.

The DMC members will meet regularly to review blinded safety data and may decide to carry out additional unblinded safety review, as necessary. In addition, the DMC members will hold two DMC meetings with review of unblinded safety data before IA1.

Laboratory personnel performing the bioanalytical PK sample analysis may receive an open randomization list to enable analysis of relevant samples prior to IA2. In addition, a PK analyst and modelling/simulation scientist may receive an open randomization list to enable preparation of modelling/simulation activities. These individuals will not interact with site or CRO personnel, who is blinded.

For the second unblinded IA, all investigators and subjects will remain blinded to treatment assignments. Once the second interim database lock has occurred after the last subject completed the visit at Week 24 or early discontinued before Week 24 and all data up to Week 24 are cleaned, the study statistician, statistical programmers and designated sponsor team members will be unblinded to perform and/or review analysis of key study endpoints (please refer to the unblinding plan for further details). All sponsor or CRO personnel in direct contact with study sites will remain blinded and be firewalled to prevent accidental unblinding. The second interim analysis will consist of all planned analyses described in Table 2.1. It will present data for all subjects up to Week 24 (Visit 13) that is the minimum analysis cutoff visit for interim 2 and data beyond Week 24 (please refer to Table 4.4 for

further details about the imputation methods). The exact cut-off date for IA2 will be specified at a later stage before unblinding.

Table 2.1 List of assessments and timeframes analyzed for interim analyses

Purpose	Assessment	Timeframe	
		Interim 1	Interim 2 ^a
Subject Status	Subject demographics and other baseline characteristics	Screening/ Baseline	Screening/ Baseline
	Analysis populations and/or subject disposition	Up to Week 12	> Week 24
	Medical history, previous and concomitant medications	N/A	> Week 24
	Treatment compliance and/or treatment exposure	Up to Week 12	Up to Week 24
	Protocol deviations	Up to Week 12	Up to Week 24
Efficacy	IGA response: proportion of subjects achieving an IGA score of 0, 1 with an IGA reduction of at least 2 points from baseline (primary endpoint at Week 12)	Up to Week 12	> Week 24
	Proportion of subjects achieving PASI 75/PASI 90/PASI 100	Up to Week 12	> Week 24
	Shift analysis from baseline in IGA	Up to Week 12	Up to Week 24
	Time to first IGA response	N/A	> Week 24
	Absolute change and percent change from baseline in PASI	Up to Week 12	> Week 24
	Absolute change from baseline in percentage of total BSA affected by psoriasis	N/A	> Week 24
	Subgroup analyses	N/A	Up to Week 24
Exploratory Analyses	Exploratory analyses after Week 12	N/A	> Week 24
	Exploratory analyses after Week 24	N/A	> Week 24
	Analyses of Quality of Life (QOL) data	N/A	Up to Week 24
PK Analyses	PK and immunogenicity analyses	N/A	Up to Week 24
Safety and Tolerability	Absolute change from baseline in vital signs and/or vital signs abnormalities and absolute change from baseline in ECG and/or ECG abnormalities	Up to Week 12	> Week 24
	Clinically laboratory abnormalities	Up to Week 12	> Week 24
	Adverse events (TEAE, serious TEAE, AESI)	Up to Week 12	> Week 24
	Mortality and suicidality and self-injurious behavior	Up to Week 12	> Week 24
	Subgroup analyses	N/A	Up to Week 24
	Any other safety data that may deemed required at the time of IA1/IA2	Up to Week 12	> Week 24

^a: For IA2, the data presented will be all data up to a cutoff date, which is beyond Week 24 (Visit 13) for the last subject unless specified otherwise. This list of planned analyses for IA2 will be confirmed before unblinding at Week 24.

Information that may unblind the study during the interim analyses must not be reported to study sites or any blinded teams as per the separate unblinding plan until the study has been unblinded.

3 Analysis Populations

For purposes of analysis, the following populations are defined:

Population	Description
Enrolled	All subjects who sign informed consent.
Intent-to-Treat (ITT)	
The Intent-to-Treat (ITT) population includes all subjects randomly allocated to a treatment.
 
Subjects will be analyzed according to planned treatment in the induction period (up to Week 12).

Modified Intent-To-Treat (MITT) including MITT12, MITT24 and MITT48	
The Modified Intent-to-Treat up to Week 12 (MITT12) population includes all subjects in the ITT population who receive at least one injection, have a baseline, and at least one post-baseline efficacy assessments up to Week 12.
 
Two additional MITT populations will be defined for exploratory analyses after Week 12 and after Week 24:
 
 • MITT24 that includes all MITT12 subjects who received at least one injection during the escalation/maintenance period from Week 12 to Week 24, • MITT48 that includes all MITT12 subjects who received at least one injection during the response assessment/dose hold period from Week 24 to Week 48. 
Subjects will be analyzed according to planned treatment:
 
 • in the induction period (up to Week 12) for MITT12, • in the maintenance/escalation period (from Week 12 to Week 24) for MITT24, • in the response assessment/response hold period (from Week 24 to Week 48) for MITT48.
Per-Protocol (PP) including PP12, PP24 and PP48	
The Per-Protocol (PP) population includes all subjects in the MITT population who have no important clinical protocol deviations affecting the assessment of efficacy.
 
Three PP populations will be defined:
 
 • PP12 population: PP population up to Week 12 including subjects in the MITT12 population • PP24 population: PP population up to Week 24 including subjects in the MITT24 population • PP48 population: PP population up to Week 48 including subjects in the MITT48 population.

Population	Description
Per-Protocol (PP) including PP12, PP24 and PP48	
The PP populations up to Week 12 and Week 24 will be defined during the blinded data review meeting prior to unblinding at Weeks 12 and 24 respectively. Membership of the PP population after Week 24 will be determined based on new protocol deviations occurring after Week 24.
 
Subjects will be analyzed according to planned treatment:
 
 • in the induction period (up to Week 12) for PP12, • in the maintenance/escalation period (from Week 12 to Week 24) for PP24, • in the response assessment/response hold period (from Week 24 to Week 48) for PP48.
Safety	
The Safety population includes all subjects who receive at least one dose of study treatment.
 
The Safety population will be analyzed per the actual treatment received using a conservative approach that will be described further in Section 4.1.

Pharmacokinetic (PK)	
The Pharmacokinetic (PK) population includes all subjects who receive at least one dose of M1095 with valid (i.e. not flagged for exclusion) PK data and with no occurrence of important protocol deviation impacting the PK results during the study.
 
The PK population will be analyzed per the actual treatment received.

Table 3.1: Definition of Analysis Populations

The primary population for efficacy data will be the ITT population. The primary analysis will be repeated on the M12 and PP12 analysis populations.

Safety data will be analyzed using the Safety population and PK data using the PK population.

All protocol deviations (PDs) will be tracked and their categorization will be reviewed and evaluated during the blinded data review meetings. Important PDs are defined as deviations from the protocol that are likely to have an impact on the subject's rights, safety, well-being, and/or on the validity of the data for analysis. However, only selected clinically important PDs affecting the assessment of efficacy will be excluded from statistical analyses in the PP populations (refer to the supplement to the SAP: Protocol Deviations Exclusion List).

The PP12 and PP24 populations and the PK population will be finalized during the blinded data review meetings.

The precise list of important PDs will be documented and approved at Weeks 12 and 24 before unblinding and at Week 48.

4 Statistical Methods

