### **9.5.1 Data Monitoring Committee (DMC)**

An independent Data Monitoring Committee (DMC) will be established to closely monitor the safety and tolerability data throughout the study and review interim analyses during the study. The DMC will be operational prior to enrolment of the first subject into the study. The composition and operation of the DMC will be described in a DMC charter. The charter will also detail how the communication between the DMC and the sponsor will be firewalled to preserve the blinding and integrity of the study.

This document must not be used to support any marketing authorization application or any variation or extension of such application

REDACTED COPY

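### Table 2.1 stops every safety output of the first interim at Week 12, so that package leaves out later safety data already accrued, including essentially all M1095 follow-up in Arm 1

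*SAP*

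**What the plan says.** SAP Section 2 defines the trigger: "the first unblinded IA of complete 12-week data for all randomized subjects will occur at the end of the induction period", with the study still running. It gives the aim as follows: "The purpose of both interim analyses is to closely monitor the safety and tolerability data throughout the study". Protocol Section 9.5.1 gives the DMC a matching remit; it is "established to closely monitor the safety and tolerability data throughout the study and review interim analyses during the study".

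Table 2.1 then sets the timeframes. In the Interim 1 column, Week 12 is the limit for vital signs and ECG, for "Clinically laboratory abnormalities", for adverse events, for "Mortality and suicidality and self-injurious behavior", and for "Any other safety data that may deemed required at the time of IA1/IA2". Safety subgroup analyses are not produced at IA1. In the Interim 2 column those same five rows run past Week 24, and footnote a supplies the rule: "For IA2, the data presented will be all data up to a cutoff date". No such rule is given for IA1.

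The SAP also gives the DMC other looks: regular blinded safety reviews, two meetings with unblinded safety data before IA1, and further unblinded review if the members want it (Section 2). Protocol Section 8.4 likewise provides for unblinded access with scheduled and ad hoc reviews.

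**The concern.** A Week 12 cut is right for the primary endpoint and for the placebo-controlled safety comparison. It is a poor rule for a package whose stated purpose is safety monitoring. IA1 waits for the last subject, so everyone enrolled earlier has passed Week 12 by then. A death or serious event at Week 16 that is already recorded has no place in the IA1 tables, and the one row that could have admitted it carries the same limit.

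The data left out are the newest exposure. Arm 1 receives its first M1095 dose at Week 12. Subjects escalated from 30 mg or 60 mg receive their first 120 mg dose at Week 12. The only earlier psoriasis study the protocol describes gave three doses over about a month to 33 M1095 subjects (Protocol Section 2.3), so the later weeks of treatment are those with least prior experience. At stake is whether an arm-specific signal in already collected data reaches the DMC in the unblinded package prepared for it.

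**Working it through.** The documents give no accrual period and no figure for follow-up at IA1, so there is no figure to reproduce. The first part is a reading of the tables, and the second is an illustration under stated assumptions.

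**What the IA1 tables contain**

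| Exposure | In the IA1 safety tables? |
|---|---|
| Weeks 0-12, all six arms | Yes |
| Escalated subjects, Weeks 0-12 on 30 mg or 60 mg | Yes |
| Escalated subjects, 120 mg from Week 12 | No |
| Arm 1, M1095 120 mg from Week 12 | No, apart from the edge case below |
| All other treatment beyond Week 12, including any dose hold | No |

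Edge case: under SAP Section 4.9.2.5 the induction window for treatment-emergent events includes the date of the Week 12 visit. An Arm 1 event on the day of the first M1095 dose could therefore be counted, but under the Placebo label of Table 4.2.

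**How much follow-up this could be**

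Inputs from the documents are 300 subjects at about 50 per arm, IA1 when the last subject reaches Week 12, and study end at Week 52, which leaves at most 40 weeks after Week 12. Assumptions are uniform accrual over A weeks, no dropout, no cleaning lag, and a data cut on the day the last subject reaches Week 12.

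A subject's post-Week 12 time at the cut is min(U, 40), with U uniform on (0, A). Its mean m is:
- A ≤ 40: m = A/2
- A > 40: m = [40²/2 + 40(A − 40)]/A, so for A = 52, m = (800 + 480)/52 = 24.6 weeks

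The share of accrued follow-up left out is m/(12 + m). Subject-years left out are n × m/52.18, with n = 300 for all arms, 50 for Arm 1, and 250 for Arms 1-5 (everyone who has started M1095).

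| Accrual A (weeks) | m (weeks) | Share left out | All arms (subject-years) | Arms 1-5 (subject-years) | Arm 1 (subject-years) |
|---|---|---|---|---|---|
| 12 | 6.0 | 6/18 = 33% | 34.5 | 28.7 | 5.7 |
| 26 | 13.0 | 13/25 = 52% | 74.7 | 62.3 | 12.5 |
| 40 | 20.0 | 20/32 = 62.5% | 115.0 | 95.8 | 19.2 |
| 52 | 24.6 | 24.6/36.6 = 67% | 141.5 | 117.9 | 23.6 |

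For comparison, the M1095 follow-up that the IA1 tables do show is Arms 2-5 over Weeks 0-12: 200 × 12/52.18 = 46.0 subject-years. With accrual of 26 weeks or more, the M1095 follow-up left out exceeds what is shown.

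Dropout and data-entry lag would lower these amounts; a cut taken later than assumed would raise them. With 12-week accrual the first subject is only at Week 24 at the cut, so dose-hold data would be close to nil.

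**The case against.** The strongest reply is that IA1 is not the DMC's only source. Two unblinded meetings precede it, blinded reviews are regular, unblinded review can be called at any time, and none of these carries a Week 12 limit. Serious events reach the sponsor within 24 hours (Protocol Section 8.5.1). The DMC charter, which is not among the documents, may already provide for cumulative unblinded tables. A reader might infer from Table 2.1 that the DMC sees no unblinded safety data after Week 12. The documents do not support that.

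The reply does not close the gap. The two meetings come before IA1, so they see fewer post-Week 12 data, and the SAP does not state their scope. An ad hoc review needs a trigger, and blinded data cannot show an imbalance between arms. For IA2 the SAP names the statistician, programmers and designated sponsor members rather than the DMC. IA1 is therefore the last unblinded DMC review that the SAP itself specifically schedules, although Protocol Section 9.5.1 gives the DMC a general role in interim analyses.

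A second reply is that the Week 12 scope is deliberate. Protocol Section 9.5 describes IA1 as an analysis of complete 12-week data, its results also go to firewalled individuals outside the DMC, and the stated purpose covers both interims taken together. This stands as a reason to keep a clean Week 0-12 package and to send anything later to the DMC alone. It also means that Table 2.1 fits poorly with the stated purpose rather than flatly contradicting it. It gives no reason to hold the DMC's own safety tables, deaths included, to Week 12.

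**Conclusion.** The point holds for the IA1 package. Every safety row produced at IA1 stops at Week 12, including deaths and the catch-all row, while the same rows at IA2 follow a cutoff date. The package therefore leaves out essentially all of Arm 1's M1095 follow-up, all data after escalation to 120 mg, and all treatment beyond 12 weeks. No available document guarantees the DMC an unblinded cumulative review of those data at IA1.

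The size is illustrative: roughly one third to two thirds of accrued follow-up for accrual of 12 to 52 weeks. It rests on uniform accrual, no dropout and no cleaning lag, and the documents supply none of these.

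It would go too far to say that escalated subjects are missing from IA1, because their Weeks 0-12 are shown, or that a signal would necessarily be missed, because other review routes exist. This is a worthwhile and inexpensive improvement to safety oversight. It does not affect the primary analysis.

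**What to change.** In Table 2.1, change the IA1 timeframe of the safety rows to all data up to a stated IA1 cutoff date, as footnote a does for IA2. Keep the Week 0-12 safety tables as the placebo-controlled comparison. Add post-Week 12 safety tables by treatment at onset, using groupings the SAP already defines in Tables 4.3 and 4.13: Arm 1 from its first M1095 dose, and escalated subjects as 120 mg from Week 12. The Data Analysis Group should deliver the added tables to the DMC only, not to the other firewalled recipients of IA1 results. Efficacy rows stay at Week 12.

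If the charter already gives the DMC unblinded post-Week 12 safety data at that time, a sentence in SAP Section 2 saying so would be enough.

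The cost is a wording change and running some programs earlier than planned. Post-Week 12 data will be less fully cleaned at IA1 and should be labelled as such. The blinding risk does not increase, because the tables stay within the existing firewall between the Data Analysis Group, the DMC and the sponsor.
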